#### **4.6 4-Month Follow-Up Visit**

All subjects will complete a follow-up visit approximately 4-months +/- 30 days (90-150 days) from the Baseline Visit.

Approximately 28 days prior to each planned subject follow-up, a PKG Watch will be ordered through the GKC Portal and dispensed to each subject as previously described. The site staff will ensure the PKG is available prior to the visit for the PKG+ Group.

Subjects in both groups will undergo the routine clinical work-up per standard of care. Protocol required data collection will occur at the visit. A Subject “ON” State Assessment will be completed and changes in medical history and medications will be recorded. Any protocol defined AEs that have occurred will be captured on the AE Reporting CRF (see Section 8). Subject surveys will be administered and include the PKG Patient Survey, PDQ-39, MDS-UPDRS, and MoCA. Medication changes (PD and other) will be updated in the corresponding medication log in the CRF.

For subjects in the PKG- Group (control group), the study investigator will complete the Clinician Assessment CRF to denote patient-reported symptoms, treatable findings, and clinical management planning based on his/her routine clinical assessment procedures. The study investigator will be blinded to the PKG information. In this group, the investigator will use clinical history and examination to determine if the subject is “controlled” or “uncontrolled.”

For the PKG+ Group, the site staff will ensure the PKG Report is available prior to the 4-Month Follow-Up Visit. A subject unable to wear a PKG Watch for at least 6 full days may be exited from the study (complete Study Completion Form) if they are unable to complete a repeat wear of the PKG Watch. The study investigator will review and report on the PKG prior to the visit and use the information to guide the discussion with the subject during the clinical assessment. The PKG will be used to determine if the subject is “controlled” or “uncontrolled.” PKG results will be recorded in the PKG Reporting CRF. The study investigator will complete the Clinician Assessment CRF to denote patient-reported symptoms, treatable findings, and clinical

**TARGET-PD**

management planning based on his/her routine clinical assessment procedures along with the PKG information.

	Target Range
Bradykinesia Score (BKS)	Median BKS 23-25 and/or FDS > 7.5
Dyskinesia Score (DKS)	Median DKS 7-9 and FDS < 13

**4.7 Annual Follow-Up Visits**

All subjects will undergo annual follow-up clinic visits at 12 months (+/- 2 months), 24 months (+/- 2 months) and 36 months (+/- 2 months) following the Baseline Visit.

Approximately 28 days prior to each planned subject follow-up, a PKG Watch will be ordered through the GKC Portal and dispensed to each subject as previously described. The site staff will ensure the PKG is available prior to the Annual Follow-up Visit. Protocol required data collection will occur at each follow-up. A Subject “ON” State Assessment will be completed and changes in medical history and medications will be recorded. Any protocol defined AEs that have occurred will be captured on the AE Reporting CRF (see Section 8). All subjects will complete a PKG Patient Survey, PDQ-39, MDS-UPDRS and MoCA.

For subjects in the PKG+ Group, the study investigator will review the PKG prior to the visit and use the information to guide the discussion with the subject during the clinical assessment. Treatment decisions based on the PKG results will be recorded in the PKG Reporting CRF. The study investigator will complete the Clinician Assessment CRF to denote patient-reported symptoms, treatable findings, and clinical management planning based on his/her routine clinical assessment procedures along with the PKG information.

If a subject requires medication changes in between annual follow-up visits, interim visits will be conducted per clinic standard of care. If medication changes are made, these will be documented in the Medication log and on the Clinician Assessment CRF.

**Table 1. Schedule of Events**

Study Activity	Screening	Baseline (28 days; +/- 7 days)	Interims (Up to 3 visits)	Follow-Up (4 month +/- 30 days)	Annual follow-ups (1, 2, 3 year +/-2 months)
Visit Type	In-clinic or phone per standard of care	In-clinic 21-35 days	In-clinic or phone per standard of care	In-clinic 90-150 days	In-clinic
Medical History	X				

**TARGET-PD**

ICF	X				
Subject Selection Criteria	X				
Randomization	X				
Clinical Management Plans		X	X	X	X
PD and Other Medications	X	X	X	X	X
AE collection (protocol defined only)		X	X	X	X
PKG Scores (provided for PKG + Group)		X	X	X	X
MDS-UPDRS I, II, III, IV and Total Score		X		X	X
MoCA	X			X	X
PDQ-39		X		X	X
PKG Patient Survey				X	X

## 5.0 Endpoints

### 5.1 Primary Endpoint

The change in MDS-UPDRS Total score at 4 months from baseline defined as sections I, II, III and IV in PwP. The endpoint will be compared between those who are treated with standard of care and PKG data (PKG+ Group) and those who are treated per standard of care alone (PKG-Group).

Subjects will be assessed in the ON state.

### 5.2 Secondary Endpoints

Secondary endpoints will include measurements as indicated below:

- Percent “responders” for MDS-UPDRS Total score (based on a minimum clinically important change of >4 points)
- Change in motor endpoints at 4 months, 1, 2, 3, years including:
  - MDS-UPDRS Part III;
  - PKG Bradykinesia score (BKS),

**TARGET-PD**

- PKG Dyskinesia score (DKS) and measurement of OFF time
- Change in PDQ-39 from baseline to 4 months, 1, 2, 3 years
- Change in MDS-UPDRS Total score from baseline to 1, 2, 3 years
- Change in MDS-UPDRS Part I from baseline to 4 months, 1, 2, 3, years
- Change in MDS-UPDRS Part II from baseline to 4 months, 1, 2, 3, years
- Change in MDS-UPDRS Part IV from baseline to 4 months, 1, 2, 3, years
- Change in PKG Scores including BKS, DKS, PTT, FDS and PTI from baseline to 4 months, 1, 2, 3 years
- Change in LED from baseline to each interim visit and 4 months, 1, 2, 3 years
- PKG Patient Survey at 4 months, 1, 2, 3, years

Subjects will be assessed in the ON state as applicable.

### 5.3 Ancillary Endpoints

Ancillary endpoints will include measurements as indicated below:

- Rate of protocol defined adverse events affecting health care utilization including: hospitalizations, emergency department, urgent care or unanticipated clinic visits from baseline to 4 months, 1, 2, 3 years follow-up
- Rate of protocol defined adverse events and potential contraindications for increasing dopaminergic therapy including: falls, orthostatic hypotension, bothersome hallucinations, delirium, and impairment that prohibits interaction with the PKG watch from baseline to 4 months, 1, 2 3 years follow up
- Rate of enrolled subjects in PKG + group who are unable to be brought into Target Range through follow-up visits

## 6.0 Statistical Methods

### 6.1 Hypothesis

The primary endpoint of change in total MDS-UPDRS will be compared between the treatment group (PKG+ Group) and the control group (PKG- Group) based on a two-sample t-test. In the event normality assumptions are violated, a non-parametric analog will be used. A difference between groups of 5 points is assumed for the change in total MDS-UPDRS as well as a standard deviation of 13 based on historical data. With these assumptions, a sample size of 280 evaluable subjects will provide approximately 83% power for the statistical hypothesis test for the primary endpoint. To account for attrition of up to 20%, a total enrollment of 350 subjects is planned.

The difference in the primary endpoint between randomized groups will be compared with a two-sample t-test of means at the 1-sided alpha of 0.025 (equivalent to a two-sided 0.05 alpha level). In the event normality assumptions are violated, a non-parametric analog will be used.

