Statistical Methods	
The primary endpoint of change in total MDS-UPDRS will be compared between the treatment group (PKG+ Group) and the control group (PKG- Group) based on a two-sample t-test. In the event normality assumptions are violated, a non-parametric analog will be used. A difference between groups of 5 points is assumed for the change in total MDS-UPDRS as well as a standard deviation of 13 based on historical data. With these assumptions, a sample size of 280 evaluable subjects will provide approximately 83% power for the statistical hypothesis test for the primary endpoint. To account for attrition of up to 20%, a total enrollment of 350 subjects is planned.
 
The primary analysis will be based on the intent-to-treat (ITT) population defined as all randomized subjects analyzed according to the treatment group assigned. Except where otherwise specified, the following general principles apply to the planned statistical analyses. All statistical analyses will be conducted using SAS version 9.4 or later (SAS Institute Inc., Cary, NC) or other widely-accepted statistical or graphical software as required. Continuous variables will be summarized with mean, standard deviation, median, max, min, and number of evaluable observations. Categorical variables will be summarized with frequency and percentages. Confidence intervals may be presented where appropriate using the t-distribution for continuous variables and Clopper-Pearson Exact method for categorical variables. Unless otherwise specified, statistical analyses will be performed using a one-sided 0.025 alpha level.

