## 6.4 Analysis Plan Overview

Interim analyses will be performed after approximately 100 and 200 subjects have been randomized and followed through the 4-month follow-up period.

The primary endpoint will be compared between those who are treated with standard of care and access to the PKG (PKG+ Group) and those who are treated per standard of care alone (PKG- Group) via a two-sample t-test. Except where otherwise specified, the following general principles apply to the planned statistical analyses. All statistical analysis will be conducted using SAS version 9.4 or later (SAS Institute Inc., Cary, NC) or other widely-accepted statistical or graphical software as required. Continuous variables will be summarized with mean, standard deviation, median, max, min, and number of evaluable observations. Categorical variables will be summarized with frequency and percentages. Confidence intervals may be presented where appropriate using the t-distribution for continuous variables and Clopper -

Pearson Exact method for categorical variables. Unless otherwise specified, statistical analyses will be performed using a one-sided 0.025 alpha level.

Additional analyses will be conducted to adjust for key baseline characteristics associated with either outcome or group assignment. A subset analysis related to falls per the ancillary endpoint will be performed at selected sites. These analyses will be performed using linear regression with primary predictor of group assignment and outcome of change in Total MDS-UPDRS, and further detailed in the study Statistical Analysis Plan.

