3.2. Hypothesis & Primary Endpoint

Primary Endpoint: The change in MDS-UPDRS Total score at 4 months from baseline defined as sections I, II, III and IV in PwP. The endpoint will be compared between those who are treated with standard of care and PKG data (PKG+ Group) and those who are treated per standard of care alone (PKG- Group).

The primary endpoint of change in total MDS-UPDRS at 4 months will be compared between the treatment group (PKG+ Group) and the control group (PKG- Group) based on a two-sample t-test. In the event normality assumptions are violated, a non-parametric analog will be used. A difference between groups of 5 points is assumed for the change in total MDS-UPDRS as well as a standard deviation of 13 based on historical data. With these assumptions, a sample size of 280 evaluable subjects will provide approximately 83% power for the statistical hypothesis test for the primary endpoint. To account for attrition of up to 20%, a total enrollment of 350 subjects is planned. Enrollment was stopped in the study at 41 subjects enrolled. These 41 subjects will be followed through the 4-month endpoint and will be analyzed.

The difference in the primary endpoint between randomized groups will be compared with a two-sample t-test of means at the 1-sided alpha of 0.025 (equivalent to a two-sided 0.05 alpha level). In the event normality assumptions are violated, a non-parametric analog will be used.

The primary analysis will be based on the intent-to-treat (ITT) population defined as all randomized subjects analyzed according to the treatment group assigned. Except where otherwise specified, the following general principles apply to the planned statistical analyses. All statistical analyses will be conducted using SAS version 9.4 or later (SAS

Institute Inc., Cary, NC) or other widely-accepted statistical or graphical software as required. Continuous variables will be summarized with mean, standard deviation, median, max, min, and number of evaluable observations. Categorical variables will be summarized with frequency and percentages. Confidence intervals may be presented where appropriate using the t-distribution for continuous variables and Clopper-Pearson Exact method for categorical variables. Unless otherwise specified, statistical analyses will be performed using a one-sided 0.025 alpha level.

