4.1. Sample Size

Based on the original planned sample size, approximately 350 subjects were to be consented to provide an estimated 280 subjects followed through the 4-Month follow-up period (assuming 20% attrition). However, enrollment was stopped in the study at 41 subjects enrolled prior to any protocol defined interim analysis milestones being achieved. These 41 subjects will be followed through the 4-month endpoint and will be analyzed.

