5.1.1. Descriptive Statistics

Continuous variables will be summarized with mean, standard deviation, median, max, min, and number of evaluable observations. Categorical variables will be summarized with frequency and percentages. Confidence intervals may be presented where appropriate using the t-distribution for continuous variables and Clopper - Pearson Exact method for categorical variables.

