Apomorphine	X 10 (total mg per day)	"When entering dose, consider total mg infused per day"
Bromocriptine	X 10	
Pergolide	X 100	
Benzhexol	No L-dopa equivalent	

Benzotropine	No L-dopa equivalent	
Biperiden	No L-dopa equivalent	

Tomlinson et al. Systematic Levodopa Equivalent Review in Parkinson's Disease. *Movement Disorders* (2010).

Rytary Instructions for Use Label – Table 1

8. Appendix 2 – Statistical Tables (see attachment)

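### The stated 83% power for 280 evaluable subjects does not follow from the stated inputs, which give about 89%

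*Protocol*

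**What the plan says.** Protocol 6.1 gives a full set of planning inputs for the primary endpoint, the change in MDS-UPDRS Total at 4 months. They are a between-group difference of 5 points, an SD of 13 attributed to historical data, and groups "compared with a two-sample t-test of means at the 1-sided alpha of 0.025 (equivalent to a two-sided 0.05 alpha level"). Randomization is 1:1 (protocol 4.3). The section concludes: "With these assumptions, a sample size of 280 evaluable subjects will provide approximately 83% power for the statistical hypothesis test for the primary endpoint". Enrollment of 350 is then derived from 20% attrition.

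The Protocol Summary (Statistical Methods) repeats the claim that "a sample size of 280 evaluable subjects will provide approximately 83% power", and SAP 3.2 carries the same inputs and figure forward. Both protocol 6.1 and SAP 3.2 allow a non-parametric test if normality fails.

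Protocol 6.4 adds: "Interim analyses will be performed after approximately 100 and 200 subjects have been randomized and followed through the 4-month follow-up period". It gives no stopping boundary or alpha adjustment, and no section links these looks to the power figure.

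SAP 3.2 then reports: "Enrollment was stopped in the study at 41 subjects enrolled". It keeps the same test for those subjects. SAP 4.1 presents the larger numbers as history: "Based on the original planned sample size, approximately 350 subjects were to be consented". On intervals, SAP 5.1.1 says: "Confidence intervals may be presented where appropriate using the t-distribution for continuous variables"; SAP 3.2 has the same optional wording. SAP Appendix 2 is only a pointer, "Statistical Tables (see attachment"), and the tables are not in the text available.

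**The concern.** The power sentence presents 83% as the consequence of the inputs just listed. A standardized difference of 5/13 = 0.385 with 140 per arm should give close to 90% power at two-sided 0.05, so 83% looks too low. If it is, either the result is wrong or one of the inputs (alpha, SD, difference, number evaluable) is not the one actually used. A reader cannot tell which.

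The stakes are limited. Understated power does not leave the planned trial too small, and the 280-subject design was never carried out. What is affected is whether the design can be reported accurately, since the same unreproducible figure stands in three places and the SAP, written after enrollment closed, did not correct it.

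A related secondary matter is how a result from about 41 subjects will be read. The SAP does not claim 83% power for 41. With so few subjects, though, a non-significant p-value alone does not tell a reader whether the 5-point design effect has been excluded.

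**Working it through.** **Inputs**

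- Difference 5, SD 13, 280 evaluable: protocol 6.1, Protocol Summary, SAP 3.2.
- Allocation 1:1 (protocol 4.3), so 140 per arm.
- Two-sample t-test, one-sided alpha 0.025: protocol 6.1, SAP 3.2. The two-sided 5% level in SAP 5.2 uses the same critical value.

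**Attempt to reproduce 83%**

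1. Standard error = SD × √(1/n₁ + 1/n₂) = 13 × √(2/140) = 1.554.
2. Noncentrality = 5 / 1.554 = 3.218, with df = 278.
3. Critical value t(0.975, 278) = 1.969.
4. Power = P(T > 1.969) for noncentral t with df 278 and noncentrality 3.218 = **0.894**.
5. Normal approximation: Φ(3.218 − 1.960) = 0.896.

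The stated 83% is not reproduced.

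**What would give about 83%** (one input changed at a time, noncentral t)

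| Change | Power |
|---|---|
| 116 per arm (232 evaluable) | 0.831 |
| 115 per arm (230 evaluable) | 0.827 |
| One-sided alpha 0.0125 | 0.832 |
| SD 14.31 | 0.830 |
| Difference 4.54 | 0.829 |

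The alpha row is what results if 0.025 is entered as a two-sided level. That is a plausible slip, but it is inference: the documents do not say so, and their stated alpha contradicts it.

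**Other features of the plan**

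- Rank test at a single look, approximated by multiplying n by an assumed relative efficiency: 0.955 (normal data) gives 0.880; 0.864 gives 0.846.
- Uneven split of the 280: 130/150 gives 0.892; 120/160 gives 0.888.
- Interim looks at 100, 200 and 280, simulated with expected Z = 5√N/26 (1.923, 2.720, 3.218) and overall two-sided 0.05. The boundaries are assumed, since none is stated. O'Brien-Fleming type gives 0.89, Pocock 0.85, and Bonferroni over three looks 0.82. Pocock combined with rank efficiency 0.955 gives about 0.83.
- Attrition: 280 / (1 − 0.20) = 350. This step is correct.

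**Secondary: the truncated trial** (SD 13, difference 5, one-sided 0.025; splits assumed)

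Half-width = t(0.975, df) × 13 × √(1/n₁ + 1/n₂).

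| Evaluable | Half-width of 95% CI | Power |
|---|---|---|
| 41 (20/21) | 2.023 × 4.062 = 8.2 | 0.224 |
| 33 (16/17; assumes 20% not evaluable) | 2.040 × 4.528 = 9.2 | 0.187 |

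If the true difference were 0, simulation of 2 million trials at 20/21 shows that about 79% of the two-sided non-significant ones have a 95% CI containing 5 and about 21% do not. Conditioning on one-sided non-significance gives about 77% and 23%.

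**The case against.** The strongest counter-argument is that 83% may not be a mistake. The protocol plans two interim analyses and a non-parametric fallback, and both lower power below 89.4%. A Pocock boundary gives about 85%, and with a rank test about 83%. A Bonferroni split over three looks gives about 82%. An allowance of this kind could have been built in and left out of the text. For the same reason 89% is a single-look, t-test figure, and with an efficacy boundary it would overstate planned power by up to about 4 points under Pocock.

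This stands in part. The origin of 83% is unknown, so a missing basis is as possible as an arithmetic slip. It does not rescue the sentence, which attributes 83% to inputs that do not produce it. No boundary or adjustment appears in the documents, and O'Brien-Fleming-type looks would leave power at about 89%.

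It is also fair that nothing in the executed trial depends on this. The shortfall is conservative, and SAP 3.2 reports the stop at 41 directly after the 350 figure, so relabelling there adds little.

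On the interval, the planned means and SDs would let a reader compute it if they are given by arm, and the unseen Appendix 2 tables may already include it. That part is therefore a low-cost suggestion, not a demonstrated gap.

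**Conclusion.** The concern holds. The stated inputs give 89.4% power, not about 83%. That gap of about 6 points is more than the word approximately can cover, and it recurs in all three places. This rests on the stated difference, SD, alpha and t-test, equal arms, and one analysis without interim adjustment. Modest imbalance does not change it.

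Severity is minor. The figure errs on the conservative side and the 280-subject design was superseded when enrollment closed. What caused the discrepancy cannot be settled from the documents.

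For the truncated trial, power for the 5-point difference is about 22% with 41 evaluable and about 19% with 33, assuming SD 13 still applies. The expected interval extends about 8 to 9 points on either side, so a non-significant result will often, but not always, leave 5 points within it. The interval shows which case applies.

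**What to change.** - In the Protocol Summary, protocol 6.1 and SAP 3.2, state the alpha, interim adjustment or SD that produced 83%. If there is none, restate planned power as about 89% at one-sided 0.025, identified as the t-test figure for a single analysis.
- In SAP 3.2, label 280 and 350 as the original plan, as SAP 4.1 already does.
- Secondary: for the primary between-group difference, make the 95% confidence interval a commitment instead of an option, unless the Appendix 2 tables already require it. Say which interval will accompany the non-parametric test if that is used.

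The cost is wording only. Test, alpha, analysis set and sample size stay as they are. Establishing the basis of 83% requires the sponsor's original sample-size calculation, which is not in the documents.

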## 6.2 Total Sample Size

Approximately 350 subjects will be consented to provide an estimated 280 subjects followed through the 4-Month follow-up period (assuming 20% attrition).

Initial sample size has been generated on currently available information and may be revised mid-study as new information external to the trial becomes available. As noted by FDA guidance (<https://www.fda.gov/downloads/drugs/guidances/ucm201790.pdf>), this approach does not raise issues of bias or concern if the interim comparative trial data is blinded and the sole source of changes to the sample size is external information. The independent Clinical Trial Steering Committee will be responsible for reviewing the data, recommending a go-forward decision and ensuring minimization of bias.

## 6.3 Statistical Analysis

### Analysis Populations

The primary analysis will be based on the intent-to-treat (ITT) population defined as all randomized subjects analyzed according to the treatment group assigned.

In addition, analyses based on the per-protocol (PP) population and the modified intent-to-treat (mITT) population will be performed for the primary and secondary endpoints. The PP population is defined as all subjects who are randomized and adhere to the study protocol requirements, including: meeting all of the subject selection criteria, completion of the PKG Watch wear period, inability for investigator to further make treatment changes due to known contraindication, completion of subject surveys and completion of follow-up visits. The mITT population is defined as all study subjects who are randomized, meet all subject selection criteria throughout the study, and complete the 3-year final study visit.

